## MATERIALS AND METHODS

### *Study subjects*

Bronchiectasis was diagnosed based on the clinical manifestations and high-resolution computed tomography scans. Patients were screened for potential eligibility at five general hospitals in Shandong Province of China from April 1, 2014 to December 31, 2016. The inclusion criteria were as follows: 1) subjects were aged 18–80 years old; 2) a diagnosis of idiopathic or post-infective bronchiectasis was made; and 3) patients had at least two exacerbations in the past year and were in a stable state for at least 4 weeks prior to the primary enrollment. Patients were excluded if they fulfilled any of the following criteria: current smokers; cigarette smoking within 6 months; cystic fibrosis or other etiologies (such as immunodeficiency, allergic bronchopulmonary aspergillosis, traction bronchiectasis caused by emphysema, advanced pulmonary fibrosis, etc.); pulmonary function test results showing a forced expiratory volume in 1 s (FEV1) ≤ 30% of the predicted value; a history of severe cardiovascular or neurological disease; comorbidity with liver disease, kidney disease, malignant tumor, gastric ulcer, or intestinal malabsorption; a known allergy to N-acetylcysteine; pregnancy or lactation (for women); a history of prior macrolide use of more than 1 week; and poor compliance. This study was registered at *ClinicalTrials.gov* (NCT02088216) and was approved by the ethics committees of the five participating hospitals. Informed consents were obtained from all patients.

### *Study design*

The Effect of N-acetylcysteine on Exacerbations of Bronchiectasis (BENE) study was a prospective, randomized, controlled, multicenter clinical trial. The main study objective was to assess whether the long-term use of oral N-acetylcysteine (600 mg, twice daily, 12 months) might reduce the incidence of exacerbations and improve the quality of life in patients with bronchiectasis. According to previous clinical data on exacerbations of bronchiectasis and the inclusion criteria that a subpopulation of bronchiectasis patients with at least two exacerbations in the past year were included in our study, we hypothesized that the baseline frequency of exacerbations was 3. Due

to the lack of clinical data on the efficiency of N-acetylcysteine in the treatment of bronchiectasis, we assumed that approximately 154 patients would need to be enrolled in this study to have 80% power to detect a reduction of at least 33% in the yearly exacerbation incidence, assuming a two-sided  $\alpha$  level of 0.05 and 20% attrition.

### **Methods**

The sequence was generated by a computer, and the patients who met the criteria were allocated in a 1:1 ratio to receive either oral N-acetylcysteine (600 mg, twice daily) or control (receive as-needed therapy) for 12 months. All the participants were followed for up to 12 months. Outpatient and/or telephone visits were obtained for the primary and secondary outcomes at 1, 3, 6, 9, and 12 months. Moreover, compliance and adverse reactions were also documented. The treatment strategy based on current guidelines was instituted for patients with exacerbations. Meanwhile, patients in the N-acetylcysteine group were also required to receive oral N-acetylcysteine (600 mg, twice daily) during the study period. For the control group, interventions would be discontinued once the patient recovered from the exacerbation. Maintenance therapies that had already started in patients with pulmonary ventilation dysfunction prior to enrollment, such as short-acting bronchodilators, long-acting bronchodilators, inhaled glucocorticoids, or theophylline, were continued during the study. However, the use of other mucolytics or expectorants, antioxidant agents, or vitamins with antioxidant properties was not recommended.

### **Study end-points**

The primary end-point was the incidence of exacerbations in a year, defined as the number of all exacerbations associated with bronchiectasis within one year. An exacerbation of bronchiectasis is defined by the British Thoracic Society guidelines for bronchiectasis. Details regarding symptoms of an exacerbation such as dyspnea, sputum volume (collected over 24 h), sputum properties, fever, and persistent upper respiratory tract infection were also documented by site investigators from all centers.

Secondary end-points included the time to the first exacerbation, 24-h sputum volume, lung function, inflammation indices, quality of life (assessed by COPD assessment test score, CAT score), and adverse events. The volume of 24-h sputum

was measured by a graduated cylinder marked in milliliters. Eligible sputum samples were used for testing sputum microbiological culture and antibiotic resistance. Pulmonary function was assessed three times before recruitment, and the maximum value was used for analysis. Following treatment, pulmonary function was reassessed for forced vital capacity (FVC), FEV1, percentage of predicted FEV1, FEV1/FVC ratio (FEV1/FVC), and inspiratory capacity, etc. Inflammatory markers including serum C-reactive protein (CRP) and the erythrocyte sedimentation rate (ESR) were tested at each visit. The severity of bronchiectasis was quantified by high-resolution computed tomography (HRCT), and the number of lobes involved was counted according to the modified Reiff grade. Furthermore, the degree of dyspnea was assessed by the modified Medical Research Council (mMRC) scale.

Effect of N-acetylcysteine on Exacerbations of Bronchiectasis (BENE): a randomized controlled trial

Official Title: Effect of N-acetylcysteine on Exacerbations of Bronchiectasis (BENE): a randomized controlled trial

Trial registration: *ClinicalTrials.gov* (NCT02088216) (Registered date: March 5, 2014)

Document Date: November 2, 2018

Statistical analyses

Patients who received at least one assessment visit after randomization were left in the original group for analysis of the results. Continuous data were expressed as the mean \pm standard deviation and were compared using the Student's *t* test. Categorical variables were expressed as a number (%) and were compared using the χ^2 test. Number of exacerbations was described by the median (interquartile range, IQR). The Mann-Whitney U test was performed to compare the difference in the number of exacerbations between the two groups. The primary study end point was the incidence of exacerbations, which is a count and follows Poisson distribution. Negative binomial regression not including other covariates was employed to compute the risk ratio and 95% confidence intervals (CIs) for N-acetylcysteine vs. the control. The time to the first exacerbation was described by Kaplan-Meier curves, and the log-rank test was used to explore the differences in time to the first exacerbation between the two groups. All analyses were conducted with the Statistical Package for the Social Sciences (SPSS) software (version 20.0). A *p* value < 0.05 was considered statistically significant.

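### Part-year follow-up is not handled in the primary exacerbation comparison: Mann-Whitney on raw counts cannot use follow-up time, and no exposure term is stated for the negative binomial model

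*SAP*

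**What the plan says.** The Protocol (Study end-points) makes the primary endpoint a one-year count, "defined as the number of all exacerbations associated with bronchiectasis within one year". Its Study design section sizes the trial on a yearly incidence and allows for 20% attrition. Under Methods it says "All the participants were followed for up to 12 months" and "Outpatient and/or telephone visits were obtained for the primary and secondary outcomes at 1, 3, 6, 9, and 12 months".

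The SAP (Statistical analyses) sets the analysis population: "Patients who received at least one assessment visit after randomization were left in the original group for analysis of the results". For the count it says "The Mann-Whitney U test was performed to compare the difference in the number of exacerbations between the two groups". It then says "The primary study end point was the incidence of exacerbations, which is a count and follows Poisson distribution", followed by "Negative binomial regression not including other covariates was employed to compute the risk ratio", with a 95% confidence interval.

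Neither document mentions an offset, person-time, an annualised rate, imputation or a completers-only rule for the count. Only the secondary time-to-first-exacerbation analysis (Kaplan-Meier and log-rank) uses a method that allows for censoring.

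**The concern.** A patient seen only at month 1 belongs to the analysis population. That patient's count covers one month, yet it stands beside counts that cover twelve. For patients followed for the full year the raw count is the endpoint; for the others it is not.

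Mann-Whitney ranks zero events in one month the same as zero events in twelve. That follows from the test as described. For the negative binomial model the matter is open: an offset is not a covariate, so the remark about covariates does not settle whether one was used.

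Two things are at stake. The first is power, which Mann-Whitney loses even when loss is the same in both arms. The second is bias, if mean observed follow-up differs by arm and the model has no offset. Unequal follow-up is possible because a daily drug is compared with as-needed therapy and no placebo is described.

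**Working it through.** **Inputs from the documents.** Control rate 3 per year, ratio 0.67 (rate 2.01), two-sided alpha 0.05, 80% power, 20% attrition, about 154 patients (Protocol, Study design). Allocation 1:1 and contacts at months 1, 3, 6, 9 and 12 (Protocol, Methods). This gives 77 per arm.

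**Assumptions, not in the documents.** Dispersion k (variance = mean + k × mean²) of 0.2, 0.5 or 1.0; loss by arm; and two timings of loss. V: last seen at month 1, 3, 6 or 9 with equal chance. U: uniform over months 1 to 12. Loss is unrelated to exacerbation risk except where stated.

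**Step 1. The plan's 154.** No dispersion or SD is given, so it cannot be reproduced from the stated inputs alone. With n per arm = (1.960 + 0.842)² × (1/3 + 1/2.01 + 2k) / (ln 0.67)²:
- k = 0: 41 per arm, 82 in total, 82/0.8 = 102.5, so 103.
- k = 0.2: 61 per arm, 122 in total, 122/0.8 = 152.5, so 153.
- k = 0.214: 62 per arm, 124 in total, 124/0.8 = 155.

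So 154 is compatible with k near 0.2. Other routes also reach it (64 per arm for a standardised difference of 0.5; 128 × 1.2 = 153.6), so it does not establish k. The point does not depend on it.

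**Step 2. Bias without an offset.** With treatment as the only term and no offset, the fitted ratio is the ratio of mean counts. Its target is

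true ratio × (mean follow-up on N-acetylcysteine / mean follow-up on control).

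The mean last contact of a lost patient is (1 + 3 + 6 + 9)/4 = 4.75 months (V) or (1 + 12)/2 = 6.5 months (U). With lost fraction d, mean follow-up is 12 − 7.25d or 12 − 5.5d months.

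| Loss, control / N-acetylcysteine | V: months, factor | U: months, factor |
|---|---|---|
| 20% / 20% | 10.55 vs 10.55, 1.00 | 10.90 vs 10.90, 1.00 |
| 18% / 22% | 10.70 vs 10.41, 0.97 | 11.01 vs 10.79, 0.98 |
| 15% / 25% | 10.91 vs 10.19, 0.93 | 11.18 vs 10.63, 0.95 |
| 10% / 30% | 11.28 vs 9.83, 0.87 | 11.45 vs 10.35, 0.90 |

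The direction can reverse. With 25% / 15% and a true ratio of 0.67, the estimate is 0.67/0.934 = 0.72 (V) or 0.67/0.951 = 0.70 (U).

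**Step 3. Power under equal 20% loss, true ratio 0.67.** Simulation with gamma-Poisson counts, 6,000 trials per scenario, standard error 0.3-0.65 points. Entries are percentages for k = 0.2 / 0.5 / 1.0.

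| Method | V | U |
|---|---|---|
| Mann-Whitney | 73 / 55 / 37 | 77 / 59 / 39 |
| Negative binomial, no offset | 80 / 65 / 50 | 83 / 70 / 51 |
| Negative binomial, offset | 86 / 70 / 53 | 86 / 72 / 54 |

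A smaller repeat run at k = 0.2 gave 75-80% for Mann-Whitney against 86-87% with the offset. The fall along each row comes from the assumed dispersion. The offset itself is worth 6/5/3 points (V) or 3/2/3 points (U) to the negative binomial model. With no loss at all, Mann-Whitney has 85/67/44% and the negative binomial model about 90/77/53%. A gap of about 5/10/9 points is therefore rank-test inefficiency, and that share is larger at higher dispersion.

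**Step 4. Type I error with no true effect** (percentages, k = 0.2 / 0.5 / 1.0).

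| Loss, control / N-acetylcysteine | Timing | Mann-Whitney | Negative binomial, no offset |
|---|---|---|---|
| 15% / 25% | V | 9 / 8 / 7 | 9 / 7 / 7 |
| 15% / 25% | U | 7 / 6 / 6 | 6 / 6 / 6 |
| 10% / 30% | V | 21 / 17 / 13 | 18 / 14 / 11 |
| 10% / 30% | U | 14 / 12 / 8 | 12 / 11 / 8 |

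With the offset the rate is 5-6% (up to 7% in smaller runs). At 18% / 22% it is 5-6% for every method.

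**Step 5. Two limits.**
- Equal mean follow-up protects the ratio, not Mann-Whitney in general. An extreme case with equal means (20% lost at month 1, 12 − 11 × 0.20 = 9.8 months; 73.3% lost at month 9, 12 − 3 × 0.733 = 9.8 months) gave Mann-Whitney a type I error of 7-8%.
- An offset does not correct loss related to risk. With 20% lost in each arm and no true effect, control losses only from the more exacerbation-prone half and N-acetylcysteine losses only from the less prone half, the offset ratio was 1.08-1.12 (V) or 1.06-1.07 (U). Type I error was 10-11% or 7-8%.

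**The case against.** The strongest reply is that the negative binomial model already carries the primary result. It follows directly on the sentence naming the primary endpoint and gives the ratio and its interval, whereas Mann-Whitney follows the descriptive median. If an offset was used, the model has no defect on this point. Outcomes could be collected by telephone, and poor compliance is an exclusion criterion (Protocol, Study subjects); both make a large imbalance less likely. If telephone contact recovers the full-year count for half of the losses at 15% / 25%, the factor is 0.97-0.98 and type I error is 5-6%.

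Much of this stands, and it rules out several stronger readings that a reader might infer:
- **That the model was fitted without an offset.** The SAP does not say so, and every no-offset figure above is conditional on it. Power loss under the plan as written is shown for Mann-Whitney only.
- **That the trial's result is biased.** The documents give no dropout by arm, so all bias figures rest on assumed imbalances.
- **That the Kaplan-Meier analysis supplies the missing follow-up time.** Time to first event needs last contact only for patients without an event. At 3 per year, (1 + 3k)^(−1/k) gives about 10%, 16% and 25% event-free over a full year for k = 0.2, 0.5 and 1.0. For the other 75-90% it needs only the first event date.

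What the reply does not remove is that the SAP never says which analysis is the primary test, names only Mann-Whitney as a test of the count, and admits part-year counts without saying how they are treated.

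**Conclusion.** The point holds as a gap in the primary analysis that should be fixed. Mann-Whitney on raw counts cannot use follow-up time, and how the negative binomial model uses it is unspecified.

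Under equal 20% loss unrelated to risk, the ratio is unbiased. Mann-Whitney has about 73-80% power against about 86% for the offset model at k = 0.2. The negative binomial model, if fitted without an offset, gives up only about 2-6 points.

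If mean follow-up differs by arm, the no-offset ratio shifts by 0.93-0.95 with slight type I inflation (15% / 25%), or by 0.87-0.90 with type I error of roughly 8-21% (10% / 30%, a stress case). These sizes depend on the assumed dispersion, timing and split of loss. Confidence is medium, because follow-up by arm would decide whether any bias exists and the documents do not give it.

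**What to change.** State that the primary test and estimate are the negative binomial model with log(time from randomisation to last contact, clinic or telephone) as an offset. Keep Mann-Whitney on raw counts as descriptive. Report person-time and annualised exacerbation rates by arm. Add one simple sensitivity analysis for the unobserved part of the year, since an offset does not correct risk-related loss; imputation at the control rate is one option among several. At the very least, say in one sentence how follow-up time enters the model and report follow-up by arm.

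The cost is one derived variable, one model statement and a small amount of extra analysis. Last-contact time should come from the record of the contacts scheduled in the Protocol (Methods). Screening ended in December 2016 and the SAP is dated November 2018. If the data have been seen, label this as a post hoc re-analysis and report it beside the analysis already done.

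### The primary analysis omits patients with no post-randomisation contact, states no follow-up-time term for those it keeps, and plans no check on either

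*SAP*

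**What the plan says.** The SAP, under Statistical analyses, gives the analysis set in one sentence: "Patients who received at least one assessment visit after randomization were left in the original group for analysis of the results". It then specifies an unadjusted negative binomial regression for the primary comparison. It mentions no offset or other exposure term, no method for missing data, no analysis of all randomised patients and no sensitivity analysis.

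The Protocol, under Methods, sets the contacts: "Outpatient and/or telephone visits were obtained for the primary and secondary outcomes at 1, 3, 6, 9, and 12 months". A telephone call therefore counts as a visit, and the first opportunity is month 1. On duration it says "All the participants were followed for up to 12 months". Patients "were allocated in a 1:1 ratio" to N-acetylcysteine "or control (receive as-needed therapy) for 12 months". Study design says that the trial "was a prospective, randomized, controlled, multicenter clinical trial"; no placebo or masking is described in either document.

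The only figure for loss is in the sample-size statement under Study design, which assumes a "level of 0.05 and 20% attrition". It is not split by arm or by time. The primary end-point, under Study end-points, is the number of exacerbations within one year.

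**The concern.** Entry to the analysis set depends on something that happens after allocation, when patients can be expected to know their arm. One arm takes tablets twice a day; the other has no regular study drug. The reasons for losing touch may therefore differ by arm. If they are also related to exacerbation risk, the patients left in the two arms are no longer comparable on the primary end-point.

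A second problem arises among the patients who are kept. The set can hold a patient with one month of observation beside a patient with twelve. A model of raw counts with no follow-up time reads the first patient's short record as a low annual count. If more patients leave early in one arm, that arm looks better whatever its true rate.

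The plan offers no way to see whether either problem occurred.

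**Working it through.** **Inputs from the documents.** Planned total about 154, allocated 1:1, so 77 per arm. Control rate: "we hypothesized that the baseline frequency of exacerbations was 3" (per year). Power 80%, two-sided alpha 0.05, 33% reduction, 20% attrition. Contacts at months 1, 3, 6, 9 and 12.

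**Assumptions.** The documents give no dispersion, no number of patients without contact, and no timing of dropout.

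**The plan's own figure, used only to find a plausible dispersion.**
- Poisson counts: n per arm = (1.96 + 0.842)² × (1/3 + 1/2.01) / (ln 0.67)² = 40.7, so 41. Dividing by 0.8 gives 52 per arm, 104 in total. The planned 154 is not reached from the stated inputs.
- Adding 2k to the variance term for negative binomial counts, 62 per arm before attrition (77 × 0.8 = 61.6) requires k ≈ 0.22. Variants of the calculation give 0.21 to 0.25.
- I use k ≈ 0.22 as the central case and k = 0.7 as a high case. The unstated variance term is a separate matter.

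**How many patients could be excluded.** 0.20 × 154 = 30.8, about 31, is the planned loss of every kind. Anyone lost after a completed contact stays in the set, so 31 is a ceiling on the planned number with no contact. I take 4, 8 and 15 of 77 in the N-acetylcysteine arm as illustrations.

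**Excluding no-contact patients when there is no true effect.** Simulation with 77 per arm, 3 events per year, gamma-distributed patient risk, exclusion in the N-acetylcysteine arm only, and a Wald test on the log rate ratio:

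| Exclusion | k | Excluded | Mean rate ratio | Two-sided error |
|---|---|---|---|---|
| Unrelated to risk | 0.22 | 4, 8, 15 | about 1.00 | 5.2 to 5.4% |
| Proportional to risk | 0.22 | 4 | 0.99 | 5.5% |
| | 0.22 | 8 | 0.975 | 5.8% |
| | 0.22 | 15 | 0.953 | 6.8% |
| Proportional to risk | 0.7 | 4 | 0.963 | 5.9% |
| | 0.7 | 8 | 0.926 | 8.5% |
| | 0.7 | 15 | 0.857 | 15.4% |

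With nobody excluded, this test rejects 5.2 to 5.3% of the time at k = 0.22 and 5.3 to 5.8% at k = 0.7.

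**A near-worst case.** Suppose the excluded fraction f has twice the rate of the rest. The rate ratio is then 1/(1 − f + 2f): 1/1.05 = 0.952 for f = 0.05 and 1/1.10 = 0.909 for f = 0.10. At 70 per arm and dispersion 0.2, the standard error is √[2 × (1/3 + 0.2)/70] = 0.123, and the two-sided rejection rates are about 7% and 12%. With gamma risk at that dispersion, removing exactly the top 5% of the arm by risk gives a ratio of 2.27 between excluded and retained patients; removing the top 10% gives 2.14. A ratio of 2 is therefore close to perfect selection of the highest-risk patients, in one arm only.

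**No exposure term.** Suppose there is no true effect, the rate is 3 per year in everyone, the control arm is fully followed, and x of 77 N-acetylcysteine patients are seen only at month 1. Each of the x contributes 3/12 = 0.25 events on average.
- x = 4: (73 × 3 + 4 × 0.25)/77 = 2.857, a ratio to 3 of 0.952.
- x = 8: (69 × 3 + 8 × 0.25)/77 = 2.714, a ratio of 0.905.

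With follow-up time in the denominator, x = 8 gives 209 events over 69 + 8/12 = 69.67 years, which is 3.00 per year and a ratio of 1.00. Equal early dropout in both arms would also give 1.00 without an offset. Here the bias needs only unequal timing of loss; those who leave need not differ in risk.

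**The case against.** The rule is milder than it may look. It requires any one visit, not the month-1 visit, and a telephone contact at any of the five time points brings a patient in. Nothing in it removes a patient for stopping tablets. Because outcomes are collected at visits, it discards essentially no recorded outcome. Those points stand, and they rule out several inferences that a reader might draw:

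- That early stoppers, or patients who miss month 1, are dropped along with their events. The text does not say this.
- That about 31 of 154 patients would be excluded. That figure is loss of every kind, and the number with no contact is not given.
- That the rule is shown to favour N-acetylcysteine, or to raise the false-positive rate to 7 to 12%. The documents show no differential loss, the bias could run either way, and those rates need near-worst-case selection.
- That the plan contradicts itself on intention to treat. The documents never use that term for this set. That patients know their arm is also an inference, from the as-needed control and the absence of any masking text.

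It can also be said that declaring all randomised patients analysed does not by itself put a patient with no follow-up into the model. That is correct: such a patient has no count, and the log of zero time is undefined. Finally, an offset is not strictly a covariate, so the SAP's wording does not forbid one. But it does not state one either.

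None of this answers the two remaining gaps: no test of the effect of losing no-contact patients, and no stated allowance for unequal follow-up among those kept.

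**Conclusion.** The point holds in limited form. The primary comparison is conditional on a post-randomisation contact, in a trial with no placebo or blinding described, and the plan has no means of testing the consequence. At the dispersion that the planned sample size implies, and with a handful of exclusions in one arm, the effect on the rate ratio is small: nil if exclusion is unrelated to risk, and about 0.99 to 0.975 under no true effect if 4 to 8 of 77 are lost in proportion to risk. It becomes material only with larger losses, high dispersion or near-perfect selection.

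The missing exposure term is at least as important. The same 4 or 8 patients, seen once at month 1 in one arm only, would move a null ratio to about 0.95 or 0.90 on raw counts. That is an illustration: the documents give neither the timing nor the balance of dropout. Both parts are weaknesses that should be repaired in the analysis plan, not demonstrated bias.

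**What to change.** 1. Keep every randomised patient with any follow-up in the assigned arm. Enter the log of time from randomisation to last contact as an offset in the primary negative binomial model.
2. Report, by arm and with reasons, the randomised patients who had no post-randomisation contact.
3. Add a sensitivity analysis that includes those patients by multiple imputation, first at their own arm's rate and then with the control-arm rate for the N-acetylcysteine arm.

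The first and third steps do different jobs. The offset corrects for partial follow-up, provided that dropout is not related to later risk within an arm; it cannot bring in patients with zero follow-up. The imputation covers those.

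The cost is a change of SAP wording, one added analysis and possibly a slightly wider interval. The planned 154 is unchanged. No new telephone calls are asked for: screening ended in December 2016, follow-up is up to 12 months, and the SAP is dated November 2018, so the contact schedule should already be over.

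### Lung function is compared by an unadjusted t test although a pre-treatment value is recorded; ANCOVA on that value would give a tighter interval from data already held

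*SAP*

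**What the plan says.** The SAP (Statistical analyses) describes continuous data by mean and "standard deviation and were compared using the Student's" t test. It names no covariate for these comparisons. Its only explicit statement about covariates, that none are included, concerns the negative binomial model for the primary end-point.

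The Protocol (Study end-points) lists the secondary outcomes: "Secondary end-points included the time to the first exacerbation, 24-h sputum volume, lung function, inflammation indices, quality of life" by CAT score, and adverse events. For lung function it describes a measurement on each side of treatment. Before: "Pulmonary function was assessed three times before recruitment, and the maximum value was used for analysis". After: "Following treatment, pulmonary function was reassessed for forced vital capacity (FVC"), followed by FEV1, percentage of predicted FEV1, FEV1/FVC, inspiratory capacity and an open-ended etc.

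Treatment lasts 12 months in both arms (Protocol, Methods: N-acetylcysteine or "control (receive as-needed therapy) for 12 months"), so the end of that period is the natural time for the reassessment. For CAT, CRP, ESR and sputum volume, the Protocol describes follow-up collection but no pre-treatment value.

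**The concern.** Lung function is usually correlated with its own earlier value. Where a pre-treatment value exists, part of the spread between patients at follow-up can be explained by it and taken out of the error term. A t test on final values ignores that information. A t test on change uses it with a fixed coefficient of 1, which over-corrects when the correlation is low. ANCOVA estimates the coefficient and so does not require a choice between the two.

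What is at stake is the width of the interval for the treatment effect on lung function. Neither the validity of the comparison nor the primary result is in question.

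**Working it through.** **Plan's own figure.** No sample size, SD or power is stated for any continuous secondary outcome, so there is no figure to reproduce for this point. The total of 154 (Protocol, Study design: "we assumed that approximately 154 patients would need to be enrolled in this study") was set for the exacerbation rate and is used here only to fix the number per arm.

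**Inputs from the documents.** 154 patients, 1:1 allocation, 20% attrition. Per arm: 154/2 × 0.8 = 61.6, taken as 61, so 122 in all.

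**Assumptions.** The correlation r between pre-treatment and post-treatment values is not in the documents; 0.3 to 0.8 is shown. SDs before and after are taken as equal, which is itself uncertain because the pre-treatment value is a maximum of three and the Protocol does not say how the post-treatment value is formed.

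**Formulas.** Variance of the treatment difference relative to a t test on final values:
- final value: 1
- change: 2(1 − r)
- ANCOVA: 1 − r²

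The ratio of ANCOVA to final value is 1 − r². The ratio to change is (1 − r²)/[2(1 − r)] = (1 + r)/2. Neither exceeds 1.

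**Small-sample cost of ANCOVA.** Average chance imbalance in the baseline multiplies the variance by 1 + 1/(2n − 4) = 1 + 1/118 = 1.0085. The t quantile moves from 1.9799 (120 df) to 1.9801 (119 df), which is negligible.

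**Example, r = 0.5.** Large sample: √0.75 = 0.866, or 13.4% narrower. With the cost: √(0.75 × 1.0085) = 0.870, or 13.0% narrower.

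| r | ANCOVA | Change | Better t test | ANCOVA / better | Narrower, large sample | Narrower, with cost | With cost, against final value | With cost, against change |
|---|---|---|---|---|---|---|---|---|
| 0.3 | 0.91 | 1.40 | final | 0.91 | 4.6% | 4.2% | 4.2% | 19.0% |
| 0.5 | 0.75 | 1.00 | equal | 0.75 | 13.4% | 13.0% | 13.0% | 13.0% |
| 0.7 | 0.51 | 0.60 | change | 0.85 | 7.8% | 7.4% | 28.3% | 7.4% |
| 0.8 | 0.36 | 0.40 | change | 0.90 | 5.1% | 4.7% | 39.7% | 4.7% |

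**In patients.** By the large-sample ratios, the better t test would match ANCOVA on 122 patients with 122/0.91 = 134, 122/0.75 = 163, 122/0.85 = 144 and 122/0.90 = 136, that is 12, 41, 22 and 14 more.

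**In power.** Take an effect of 0.511 SD, which a final-value t test would detect with 80% power at 61 per arm. By the noncentral t distribution with the imbalance factor included, ANCOVA has 83.3%, 89.6%, 97.4% and 99.6%, against 80.0%, 80.0%, 95.1% and 99.3% for the better t test. The gains are 3.3, 9.6, 2.3 and 0.3 points; the last is small partly because power is already near its ceiling.

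**When ANCOVA loses.** With the factor 1.0085, ANCOVA is less precise than final value only if r² < 0.0084 (r below about 0.09), and less precise than change only if (1 + r)/2 > 1/1.0085 (r above about 0.98). The loss is then at most about 0.4% in interval width.

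**The case against.** The best defence is that an unadjusted t test is unbiased and valid under randomisation, that the plan claims no power for any secondary end-point, and that baseline adjustment is therefore optional. That is right as to validity. It does not answer the loss of precision, which can be recovered from measurements the Protocol already describes.

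A second objection is timing. The SAP is dated November 2, 2018 and written in the past tense, and screening ended on December 31, 2016, so 12 months of follow-up would have finished around the end of 2017. An ANCOVA introduced after the data were seen, and placed above the one documented test, would itself be a post hoc choice of analysis. This stands, and the recommendation depends on it.

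A third is that the size is not determined by the documents, because r is assumed. This also stands: the result is a range. The 40% at its upper end applies only to a final-value t test with r = 0.8.

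A reader might also draw two stronger conclusions. The first is that the t test loses its 5% error rate because the SAP names neither the visit nor final value versus change, while "Outpatient and/or telephone visits were obtained for the primary and secondary outcomes at 1, 3, 6, 9, and 12 months". Each t test keeps its 5% level; inflation would come from selective reporting, and nothing in the documents shows any. For lung function only one reassessment is described, and no change score appears anywhere. The second is that all continuous outcomes should be baseline-adjusted. For CAT, CRP, ESR and sputum volume no pre-treatment value is described, so the documents do not show that adjustment is possible.

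**Conclusion.** The point holds as a minor, inexpensive improvement to one secondary end-point. The planned lung function comparison is valid but less precise than the described data allow. With 61 per arm, equal SDs and r between 0.3 and 0.8, the ANCOVA interval is about 4% to 13% narrower than that from the better of the two t tests, and about 4% to 40% narrower than that from a t test on final values. That ANCOVA is at least as precise, apart from the lost degree of freedom and chance baseline imbalance, holds whatever r is; the size of the gain depends on r, which the documents do not give. The primary end-point, its analysis and the total of 154 are unaffected. The documents do not support any finding of error-rate inflation or selective reporting.

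**What to change.** In the SAP:

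1. Compare each reported lung function parameter at the end of the 12-month treatment period by ANCOVA, with treatment and the same parameter's pre-treatment value as terms. Because several parameters are listed, either report all of them or name one, for example FEV1, as the main one.
2. If this is set before the data are seen, ANCOVA is the main analysis and the t test is supportive. If it is added afterwards, label it post hoc and report it as supportive beside the documented t test.
3. Extend the same model to CAT, CRP, ESR and sputum volume only for outcomes where a pre-treatment value was recorded.

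The cost is a few sentences and one model per parameter, which SPSS can fit. Lung function needs no new data. An analysis added late carries less weight, and the label must say so.
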